 initiated at a total daily dosage of 10 mg/kg per day.

Study design:

Type of the study: randomized controlled study.

The following data will be gathered and evaluated for all patients:

I-before intervention:

- Serum creatinine, Creatinine clearance. .1
- 24 hour urine protein, urine protein/creatinine ratio. .2
 - Urine analysis. .3
 - HBA1c. .4
 - HGB. .5
 - Uric acid and lipid profile. .6
 - Lupus serology. .7

II-after intervention: All patients will be evaluated monthly regarding:

- Serum creatinine, creatinine clearance. .1
- 24 hour proteinuria, protein/creatinine ratio. .2
- Fasting, random and postprandial glucose levels. .3
 - CNI trough level if used. .4
 - Urine analysis. .5
 - HGB level. .6
 - Uric acid, lipid profile. .7
 - Lupus serology. .8

Cardiovascular assessment: .9

ECCHO.

Atherosclerosis and vascular calcification incidence (NCCT model).

Regular measurement of blood pressure each visit.

Outcomes:

- Effect of dapagliflozin compared to placebo on eGFR. .1
- Effect of dapagliflozin compared to placebo on systolic/diastolic blood .2 pressure.
 - Effect of dapagliflozin compared to placebo on body weight. .3
- Safety of dapagliflozin vs. placebo the number of hypoglycemia .4 episodes between groups and serious adverse events.

Statistical Analysis:

Qualitative data were displayed in cross tabulations, and quantitative data were described in terms of arithmetic mean ± SD. Bivariate techniques were used for initial evaluation of contrasts. Thus, the chi-square and Fisher's exact tests were used for comparisons of frequencies of qualitative variables; the Mann-Whitney test and the unpaired t-test were used for comparisons of means of two quantitative variables. A p-value <0.05 was considered significant. Graft and patient survival rates were assessed using the Kaplan-Meier method. All analyses were carried out using the computer package SPSS for windows, release 16 SPSS Inc. Chicago, III, USA.

Administrative design •

Informed consent will be obtained from all subjects and the approval will be obtained from institutional review board (IRB) in Faculty of Medicine, Mansoura University. There is no funding.

Research question

The main research question is: Does use of SGLT2i will show superiority over conventional lines of treatment of lupus nephritis patient as regard efficacy and safety.

Rationale and justification

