
General Considerations

Significance Level: A two-sided alpha level of 0.05 will be used for all primary analyses.

Analysis Populations:

Intent-to-Treat (ITT): All randomized patients will be analyzed according to their assigned group.

Per-Protocol (PP): Only patients completing the study without major protocol violations.

Primary Endpoint Analysis

Renal Outcomes: ANOVA for repeated measures for serum creatinine and eGFR if normally distributed, and the Friedman test for non-normally distributed data. Post-hoc tests using Bonferroni correction.

Cardiovascular Outcomes: Mann-Whitney U test for BNP levels and coronary calcification between groups.

Hematological Outcomes: Paired t-test for hemoglobin and erythropoietin levels if data is normally distributed; otherwise, Wilcoxon signed-rank test.

Secondary Endpoint Analysis

Body Weight and BMI: Compared over time using ANOVA for repeated measures.

Echocardiographic Parameters: Analyzed with paired t-tests, adjusted with Bonferroni correction.

Iron Profile: Analyzed pre- and post-intervention using ANOVA or Kruskal-Wallis for non-normally distributed variables.

Categorical Variables

Chi-Square Test: For between-group comparisons of categorical data (e.g., presence of diabetes, hypertension).

7. Handling of Missing Data

Imputation: Last observation carried forward (LOCF) for data missing at random; multiple imputation for extensive missing data.

Sensitivity Analysis: Conducted to evaluate the robustness of primary endpoint findings against different missing data assumptions.

8. Interim Analysis

Timing: An interim analysis is planned at the halfway point (6 months).

Stopping Rules: An O'Brien-Fleming approach will be applied to adjust the significance threshold for interim testing, allowing for an earlier stop for efficacy or safety concerns.

9. Safety Analysis

Adverse Events (AEs): Summarized by type, frequency, and severity. Fisher's exact test will be used to compare AE rates between groups.

Specific Safety Parameters: Monitoring for hypotension, electrolyte imbalances, and kidney function.

10. Data Quality and Management

Data Quality Measures: Includes data verification, regular audits, and query resolution.

Database Lock: Data will be locked and verified prior to the final analysis.

11. Software

Statistical Software: All analyses will be conducted using SPSS (Version 25).

12. Appendices

	Control group. (n= 41)	Study group. (n= 38)	P value

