End diastolic volume; Chi square test; Student t- test; Man, Whitney test; Level of significance < 0.05.

Table (10): Comparison between both groups as regard post intervention side effects

	Control group. (n= 41)	Study group. (n=38)	P value
AKI episodes No. (%)			
- No	38 (92.7%)	31 (81.6%) 5 (13.2%)	0.17
- once	1 (2.4%) 2 (4.9%)	2 (5.3%)	
- twice			
UTI No. (%)			
- No	35 (85.4%) 4 (9.8%)	31 (81.6%) 5 (13.2%)	0.8
- once	2 (4.9%)	2 (5.3%)	
- more than once			
Gynecological infection No. (%)	1 (2.4%)	2 (5.3%)	0.6
Viral infection No. (%)	1(2.4%)	1 (2.6%)	1
MMF intolerance No. (%)	1 (2.5%)	2 (5.3%)	0.6
Renal biopsy No. (%)	2 (4.9%)	1 (2.6%)	0.6
Increase steroid dose No. (%)	7 (17.1%)	4 (10.5%)	1

UTI: urinary tract infection episodes; AKI: acute kidney injury; chi-square test for categorical data. Categorical data are expressed as number (percentage).; Level of significance < 0.05.

figure1: flow chart of participating populations

Figure (2) shows difference between individual which had improved eGFR or not as regard to their basal eGFR in total cohort, which found that improving eGFR had been occurred in patients with lower eGFR (107±50 vs 137±58 ml/min/m²

Figure (3) show no significant difference between the drug and placebo groups (p=0.857). as regard incidence of anemia before intervention, the drug group has 23 anemic participants (60.5%) versus 24 participants (58.5%) in the placebo group, while post intervention, In the anemia category, the drug group has 16 participants (42.1%), while the placebo group has 22 participants (53.7%) with non-significant differences (p = 0.3)

Figure (4) differences in body weight between both groups at different time points:

Glossary of Terms and Abbreviations

AA	Amino Acids
ABIN	A20 Binding Inhibitor Of NF-Kb
ACE	Angiotensin-Converting Enzyme Inhibitors
ACR	American College of Rheumatology
AKI	Acute Kidney Injury
ALCAM	Activated Leucocyte Adhesion Molecule
ALP	Alkaline Phosphatase
AMP	Adenosine Monophosphate
АМРК	Amp-Activated Protein Kinase
ANA	Antinuclear Antibodies
ANG II	Angiotensin 2
ANOVA	Analysis Of Variance
ANTI-DSDNA	Anti Double Stranded Deoxyribonucleic Acid
	Antibodies
ANTI-SM	Anti-Smith Antibodies
APLS	Antiphospholipid Syndrome
ARBS	Angiotensin 2 Receptor Blockers
ATN	Acute Tubular Necrosis
ATP	Adenosine Triphosphate
BAFF	B-Cell-Activating Factor
BLISS	B Lymphocyte Stimulator Inhibitor Belimumab
	Plus Standard Therapy
BMI	Body Mass Index
BNP	Brain Natriuretic Peptide
BP	Blood Pressure

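### Table 10 mixes significance tests under a chi-square footnote where SAP section 9 plans Fisher's exact test, and its steroid-increase p = 1 comes from no standard two-sided test

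*SAP*

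**What the plan says.** SAP section 9 sets the test for adverse events: Fisher's "exact test will be used to compare AE rates between groups". It does not say how rows with more than two levels (none, once, twice) are to be tested, and it plans no risk difference or confidence interval.

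Table 10, in the appendix of the same SAP, lists seven post-intervention side effects for 41 control and 38 study patients. Its footnote reads "UTI: urinary tract infection episodes; AKI: acute kidney injury; chi-square test for categorical data" and does not mention Fisher.

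Two other places bear on the choice. SAP section 6 gives chi-square as the general between-group test for categorical data, with diabetes and hypertension as examples. The protocol's statistical section allows both, saying that chi-square and Fisher's "exact tests were used for comparisons of frequencies of qualitative variables".

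On sidedness, SAP section 6 says only this: "A two-sided alpha level of 0.05 will be used for all primary analyses". Nothing is stated for safety.

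**The concern.** The plan and the table's footnote name different tests for the same comparisons. The choice matters with counts this small. As printed, six of the seven rows have a minimum expected count between 0.96 and 1.92, with at least half their cells below 5, and there the chi-square approximation is unreliable.

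Two rows stand out. "Increase steroid dose No" carries p = 1 although the proportions are 17.1% and 10.5%. "Renal biopsy No" carries 0.6 with only three events in total. The AKI row also deserves care, because section 9 names kidney function as a specific safety parameter and any AKI was recorded in 7 study patients against 3 controls.

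At stake is whether a reader can reproduce the safety p-values and knows which test produced them. No conclusion at the 0.05 level depends on it.

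**Working it through.** **Inputs.** Counts are from Table 10 (control n = 41, study n = 38, total 79). The AKI and UTI rows are broken in the extracted text. Read in order and checked against their percentages, they are AKI 38/1/2 versus 31/5/2 and UTI 35/4/2 versus 31/5/2, which sum to 41 and 38. Tests are taken as two-sided.

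**Steroid increase, 7/41 versus 4/38, printed p = 1.**
- Smallest expected count: 11 × 38/79 = 5.29, so this row is not sparse.
- Pearson: 79 × (7×34 − 4×34)² / (41 × 38 × 11 × 68) = 821,916 / 1,165,384 = 0.705 on 1 df, p = 0.40.
- Likelihood ratio 0.40; Yates 0.61; Fisher 0.52. The one-sided Fisher values are 0.31 and 0.88. None is 1.
- Table 1 has the same counts for male sex (7/41 versus 4/38) and prints 0.5, which is the Fisher value.

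**Renal biopsy, 2/41 versus 1/38, printed 0.6.**
- Pearson: 79 × (2×37 − 1×39)² / (41 × 38 × 3 × 76) = 96,775 / 355,224 = 0.272, p = 0.602. The likelihood ratio gives 0.598.
- Fisher: with 3 events among 79 patients, the probabilities of 0, 1, 2 or 3 in the control arm are 8,436, 28,823, 31,160 and 10,660, each divided by 79,079, that is 0.107, 0.364, 0.394 and 0.135. The observed 2 is the most probable outcome, so the two-sided p-value is 1.00.

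**Gynecological infection and MMF intolerance, both 1/41 versus 2/38, printed 0.6.** The margins are the same, with 1 event in the control arm: Fisher = 0.364 + 0.135 + 0.107 = 0.606. Pearson is 0.512. These two rows are Fisher values. (The 2.5% printed for MMF intolerance fits 1/40; Fisher is then 0.610, still 0.6.)

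**AKI, printed 0.17.**
- Expected counts: 35.8/3.11/2.08 and 33.2/2.89/1.92; 4 of 6 are below 5.
- Three levels: Pearson 3.268 on 2 df, p = 0.195; likelihood ratio 3.508, p = 0.173; Fisher-Freeman-Halton exact 0.256.
- Any AKI, 3/41 versus 7/38: Pearson 0.138, Yates 0.252, Fisher 0.183.
- Only the likelihood-ratio statistic rounds to 0.17.

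**All rows**

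| Row | Printed | Pearson | Fisher, levels as printed | Fisher, any vs none |
|---|---|---|---|---|
| AKI | 0.17 | 0.195 | 0.256 | 0.183 |
| UTI | 0.8 | 0.887 | 0.896 | 0.765 |
| Gynecological infection | 0.6 | 0.512 | 0.606 | 0.606 |
| Viral infection | 1 | 0.957 | 1.00 | 1.00 |
| MMF intolerance | 0.6 | 0.512 | 0.606 | 0.606 |
| Renal biopsy | 0.6 | 0.602 | 1.00 | 1.00 |
| Steroid increase | 1 | 0.401 | 0.521 | 0.521 |

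At printed precision Pearson reproduces 2 of 7 rows, Fisher on the levels as printed 3 of 7, and Fisher on any versus none 4 of 7. No single test reproduces the column.

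**Interval for any AKI.** The difference is 7/38 − 3/41 = 0.184 − 0.073 = 0.111. The Wilson 95% limits are 0.092 to 0.334 (study) and 0.025 to 0.194 (control). Newcombe's limits follow:
- lower: 0.111 − √[(0.184 − 0.092)² + (0.194 − 0.073)²] = −0.041
- upper: 0.111 + √[(0.334 − 0.184)² + (0.073 − 0.025)²] = 0.269

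The risk ratio is 2.52 (95% CI 0.70 to 9.04).

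**The case against.** A biopsy is a procedure and a steroid increase is a treatment change, so neither need be an adverse event under section 9. The general chi-square rule of section 6 would then apply, and 0.6 for biopsy would be correct. The reading is possible, but Table 10's title presents every row as a side effect, and the footnote draws no such line. It does not rescue the steroid row either, where chi-square gives 0.40.

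The AKI change is also small. Collapsed to any versus none, 0.17 becomes 0.18; the move to 0.26 appears only if three levels are kept, and section 9 does not settle that. This stands.

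A reader might infer more than the documents support:
- **That chi-square was used throughout, so the safety p-values in general are wrong.** Three rows already match Fisher as printed, and UTI matches once collapsed.
- **That sparse cells explain the steroid value.** That row has no expected count below 5.
- **That the missing AKI interval follows from the choice of test.** Fisher's p-value supplies no interval, and neither document plans one, so its absence departs from nothing.
- **That the SAP presents AKI as equal between arms, or that an excess is shown.** No text accompanying Table 10 draws the first conclusion, and an interval that includes zero does not establish the second.

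**Conclusion.** The point holds in a limited form. Section 9 and the footnote name different tests, and the printed column comes from a mixture of tests. The steroid p-value is wrong under every standard two-sided test and contradicts Table 1. The biopsy p-value departs from section 9 if the row counts as an adverse event (0.6 against 1.00). The AKI p-value is not from the planned test, although the any-versus-none Fisher value is close.

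The effect on inference is small, since every recomputed value is above 0.05. The more useful information is the AKI interval: the data are compatible with a risk from about 4 points lower to about 27 points higher on the study drug.

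This rests on two-sided testing for safety and on reading the broken AKI and UTI rows in printed order. The any-versus-none results do not depend on how once and twice are divided. One possible source of the steroid value is a row slip, since 1 is the Fisher value for the biopsy row just above; the documents do not show this.

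**What to change.** 1. Re-run all of Table 10 with two-sided Fisher's exact test, as section 9 states, on patients with at least one event.
2. Correct the p-values: steroid increase 0.52, renal biopsy 1.0, any AKI 0.18. The collapsed UTI value is 0.76.
3. Change the footnote to name Fisher's exact test, and add a sentence to section 9 saying that repeated-event rows are compared as any versus none.
4. As a separate improvement, report a risk difference with 95% CI for each row. For any AKI, give 18.4% versus 7.3%, +11.1 points (Newcombe 95% CI −4.1 to 26.9), and state that an excess of up to about 27 points is not excluded.

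The cost is one table re-run from existing counts, one footnote, and one or two sentences in the SAP.

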SLE is a chronic inflammatory disease that has renal effect in about half of patients. Lupus nephritis is a major risk factor for morbidity and mortality in patients with SLE, and in spite of strong anti-inflammatory and immunosuppressive therapies still ends in CKD or ESRD. (5)

Based on this observation, we aim to determine the effect of SGLT2i treatment in patients with glomerulonephritis secondary to SLE who either is diabetic or non-diabetic.

Aim of the work

This study aims to assess SGT2i role in regression of ongoing kidney and cardiac diseases among lupus nephritis patient either diabetic or non-diabetic under different immunosuppressive therapy.

Patients and methods

Technical design:

Study sitting: .1

Nephrology and renal transplant unit at urology and nephrology center in Mansoura University.

It will include 100 patients with lupus nephritis, Diagnosis of glomerulonephritis was performed by renal biopsy, and all of the renal biopsies were carried out at urology and nephrology center.

Patients with an estimated glomerular filtration rate (eGFR) >30 ml/min/1.73m2 will be randomized into two groups

- Study group will receive SGLT2i inhibitor as add on drug or replace
 another drug according to patient clinical situation, Dapagliflozin 10
 mg and 25 mg will be used once daily with or without food.
 - Control group will be maintained on placebo. •

The primary endpoint will be sustained decline in eGFR ≥50%, ESKD, or kidney or cardiovascular death

We will follow up all patients for 12 months and compare their results.

2. Inclusion criteria:

- Patients aged more than 16 year. .1
- Willing to sign informed consent. .2
- Diagnosis of SLE according to EULAR/ACR classification .3 criteria.
 - Renal biopsy showed lupus nephritis. .4
- Patient with eGFR > 30 ml/min/1.73m2 by cockcroft-gault .5 equation.

3. Exclusion criteria:

- Patients with eGFR <30 ml/min per 1.73 m2. .1
 - Current pregnancy or lactation. .2
- Medical history of chronic disease (CLD, cancer, severe .3 respiratory distress, gastrointestinal tract lesions).
- Patients refusing to participate in the study or lost follow up. .4
- Evidence of urinary obstruction of difficulty in voiding at .5 screening.

- Patients who are receiving high dose diuretics or combined .6 ACEI, ARBS.
- Patients who have frequent hypotensive episode or SBP .7 <100 mmHg.

Operational design:

Study Protocol:

Patients included in the study will treated with dapaglifilozin

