Statistical Analysis Plan

Document Control

Title: Statistical Analysis Plan for the Study of SGLT2 Inhibitors in Lupus Nephritis Patients

Protocol ID: [NCT05748925] Version: 1.0 Date: [11/3/2024] Principal Investigator: [[name]] Statistician: [[name]] Approval Signatures: Principal Investigator: [name] Statistician: [name]

Table of Contents

- 1. Introduction
- 2. Study Design
- 3. Study Objectives
- 4. Endpoints
- 5. Sample Size Justification
- 6. Statistical Methods
- 7. Handling of Missing Data
- 8. Interim Analysis
- 9. Safety Analysis
- 10. Data Quality and Management
- 11. Software
- 12. Appendices

1. Introduction

• **Purpose of the SAP**: This document outlines the statistical approach for analyzing data from the clinical trial studying the effects of SGLT2 inhibitors on renal, cardiovascular, and hematological outcomes in lupus nephritis patients.

2. Study Design

Design: Randomized, double-blind, placebo-controlled clinical trial.

Study Duration: Conducted from September 2022 to November 2023

Randomization: Patients were randomly assigned to either dapagliflozin (10 mg once daily) or placebo groups using computer-generated random tables in a 1:1 ratio stratified by age and gender.

Blinding: The study was double-blinded, and all trial staff and participants remained unaware of individual treatment assignments until study completion.

3. Study Objectives

Primary Objective: To evaluate the impact of SGLT2 inhibitors on renal, cardiovascular, and hematological parameters in lupus nephritis patients.

Secondary Objective: To explore changes in body weight, BMI, and other echocardiographic and iron profile parameters over 12 months.

4. Endpoints

Primary Endpoints

Renal Function: Serum creatinine, eGFR, and 24-hour urine protein

Cardiovascular Health: BNP levels and coronary calcification via NCCT

Hematological Parameters: Hemoglobin and erythropoietin levels

Hepcidin Level: Measured before and after intervention

Secondary Endpoints

Body Weight and BMI: Assessed at baseline and follow-up visits.

Echocardiographic Findings: Assessed pre- and post-intervention.

Iron Profile: Serum ferritin and TSAT

5. Sample Size Justification

Calculation: A sample size of 100 patients was targeted, accounting for potential dropouts, to provide sufficient power (80%) at a significance level of 0.05 to detect differences between the two groups.

6. Statistical Methods

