Age (years) Mean ± SD	36.6 ± 9.6	38±9.8	0.8
Sex No. (%) - Male - Female	7 (17.1%) 34 (82.9%)	4 (10.5%) 34 (89.5%)	0.5
Body weight (Kg) mean ± SD	78.9 ± 14	90 ± 15	0.5
Body mass index (Kg/m ²) mean ± SD	30.6 ± 10.5	33±5.7	0.6
Hypertension No. (%)	37 (90.2%)	38 (100%)	0.1
Diabetes No. (%)	7 (17.1%)	11 (28.9%)	0.2

Table (1): Demographics and associated medical disorders:

(Student T test or Mann-Whitney) for continuous data, and chi-square test for categorical data. Continuous data are expressed as mean (SD) or median (minimum – maximum). Categorical data are expressed as number (percentage), Level of significance < 0.05.

Table (2): SLE characteristics:

	Control group. (n= 41)	Study group. (n= 38)	P value
Disease duration (years) Median (min, max)	6 (1, 20)	7(1,19)	0.3

Lupus nephritis class No.			
(%)			
- Class I	1 (2.4%)	1 (2.6%)	
- Class II	2 (4.9%)	7 (18.4%)	0.1
- Class III	11 (26.8%)	8 (21.1%)	0.1
- Class IV	26 (36.4%)	16 (42.1%)	
- Class V	5 (2.4%)	1 (13.2%)	
- Class VI	0 (0%)	1 (2.6%)	
Activity index Median	6 (0, 10)	6 (0, 21)	0.8
(min, max)	0 (0, 19)	0 (0, 21)	0.8
Chronicity index Median	2(0, 8)	5 (0, 14)	0.2
(min, max)	2 (0, 8)	5 (0, 14)	0.2
Anti- phospholipid No.	6 (14 6%)	3 (7.0%)	0.4
(%)	0 (14.070)	5 (7.970)	0.4
Immunosuppressive			
medications No. (%)			
- Steroid + MMF	27 (65.9%)	18 (47 4%)	
- Steroid + CNI	5 (12.2 %)	4(10.5%)	0.2
- Steroid + CNI + MMF	2 (4.9 %)	1 (2 6%)	0.2
- Steroid + Azathioprine	7 (17.1%)	14(36.8%)	
- Steroid	0 (0%)	1 (2 6%)	
		1 (2.070)	
Cyclophosphamide No.	7 (17 1%)	5 (13.2%)	0.7
(%)	(1,11,0)		
Other medications No. (%)			
- Aspirin	15 (36.6%)	18 (34.4%)	0.3
- Statins	30 (73.2%)	24 (63.2%)	0.4
- Allopurinol	10 (24.4%)	14 (36.8%)	0.3
- ACEI/ARBS	26 (63.4%)	27(71.1%)	0.4
- Diuretics	14 (34.1%)	16 (32.1%)	0.3

MMF: mycophenolate mofetil; CNI: calcineurin inhibitors; ACEI/ARBS: angiotensin converting enzyme inhibitors/angiotensin receptor blockers; (Student T test or Mann-Whitney) for continuous data, and chi-square test for categorical data. Continuous data are expressed as mean (SD) or median (minimum – maximum). Categorical data are expressed as number (percentage).; Level of significance < 0.05.

	Control group. (n= 41)	Study group. (n= 38)	P value
Consumed C3 & C4 No. (%)	5 (12.2%)	2 (5.3%)	0.4

S. creatinine (mg/dL) Median (min, max)	0.8 (0.4, 2.7)	0.8 (0.4, 2.6)	0.8
24- hour urinary protein (g/24 hours) mean ± SD	0.4 (0.06-3.6)	0.6 (0.07-3)	0.3
eGFR (ml/min/m ²) mean ± SD	114 ± 51	128 ± 59.7	0.6

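### The chronicity-index row of SAP Table 2 (medians 2 v 5, p = 0.2) needs a source check; if the gap is real, no renal comparison allows for it

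*SAP*

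**What the plan says.** - Biopsy-proven disease is an entry condition (Protocol, Inclusion criteria, item 4: "Renal biopsy showed lupus nephritis").
- SAP section 12, Table 2, tabulates activity and chronicity indices by arm. The row "Chronicity index Median" reads 2 (0, 8) for control (n = 41) and 5 (0, 14) for study (n = 38), p = 0.2.
- SAP section 2 stratifies randomisation by age and gender only.
- SAP section 4 lists creatinine, eGFR and 24-hour protein as primary renal endpoints. For these, section 6 plans "ANOVA for repeated measures for serum creatinine and eGFR if normally distributed", with the Friedman test otherwise. It names no covariate, and no method for 24-hour protein.
- The footnotes to Table 6 show repeated-measures ANOVA used within each arm, and an unadjusted t or Mann-Whitney test between arms at each visit.
- The only planned sensitivity analysis (SAP section 7) concerns missing data.

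**The concern.** The chronicity index grades established scarring, so one would expect it to bear on later kidney function. If the study arm began with more scarring, part of its later eGFR and creatinine would reflect that and not the drug. Neither the design nor the analysis allows for it.

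The printed p = 0.2 does not settle the matter. A non-significant baseline test does not show that a prognostic imbalance is harmless, and here the p-value is hard to reconcile with the medians and ranges beside it. Either the imbalance is large, or a figure in the row is wrong.

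**Working it through.** The plan gives no figure for this imbalance or its effect, so there is none to reproduce. The check has four parts.

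**1. Do the medians, ranges and p-value agree?**
- SD from range / 4.3: control 8/4.3 = 1.9 (1.8 by the unrounded factor), study 14/4.3 = 3.3, pooled 2.6.
- Standardised difference from the medians: (5 − 2)/2.63 = 1.14.
- Standardised difference that matches p = 0.2: 1.28 × √(1/41 + 1/38) = 0.29.
- The two readings differ about fourfold. Of 6,170 simulated rounded-gamma samples with medians 2 and 5, clipped to the printed ranges, none gave a Mann-Whitney p of 0.15 or more; the typical p was about 0.00001. U-shaped distributions, or only 20 v 19 scored biopsies, reached 0.15 in about 1%.
- The combination is not impossible. Take control as one 0, thirty-six 2s and four 8s, and study as fourteen 0s, twenty-three 5s and one 14. The printed medians and ranges hold, and p is 0.21. That is an odd shape for such a score.
- Other entries support a source check. Weight of 78.9 ± 14 v 90 ± 15 (Table 1) gives p = 0.001 against a printed 0.5. The nephritis class counts in Table 2 sum to 45 and 34, not 41 and 38; exchanging the two class V counts restores both totals.

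**2. How far could the index move the baseline-adjusted eGFR difference?** Shift = partial r × residual SD × standardised imbalance. The partial r (0.1 to 0.4) and the residual SD after baseline adjustment (20 to 28 ml/min) are assumptions; the documents give neither. The raw imbalance in the index is used, not the part left after baseline eGFR.

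| Imbalance (SD) | r = 0.1 | r = 0.3 | r = 0.4 |
|---|---|---|---|
| 0.29 | 0.6 to 0.8 | 1.7 to 2.4 | 2.3 to 3.2 |
| 1.14 | 2.3 to 3.2 | 6.8 to 9.6 | 9.1 to 12.8 |

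Values are in ml/min, against the drug. The extremes are 0.1 × 20 × 0.29 = 0.6 and 0.4 × 28 × 1.14 = 12.8.

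**3. What pulls the other way?** Baseline eGFR is 128 in study and 114 in control, a gap of 14; at 12 months it is 115.7 and 100.3, a gap of 15.4. The mean changes are −12.3 and −13.7. With pooled SDs of 55.4 (baseline) and 46.2 (12 months) and an assumed baseline-to-12-month correlation of 0.5 to 0.9, the baseline gap favours the study arm at 12 months by 0.5 × 14 × 46.2/55.4 = 5.8 up to 10.5 ml/min.

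**4. What does adjustment do to precision?** SE ratio = √[(1 − r²)/(1 − ρ²)], where ρ² = d²/(d² + 1/(pq)), p = 41/79, q = 38/79 and 1/(pq) = 4.006.
- d = 1.14: ρ² = 1.30/5.31 = 0.245, so the SE rises by 14.5% (r = 0.1), 9.8% (r = 0.3) or 5.5% (r = 0.4). At d = 1.1 the figures are 13.5%, 8.9% and 4.6%.
- d = 0.29: ρ² = 0.021, so the SE is about unchanged at r = 0.1 and 7% lower at r = 0.4.

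**The case against.** **The 5 may not be a 5.** In the text read from the PDF, this part of Table 2 appears twice with conflicting digits. The antiphospholipid count for the study arm reads 3 in one copy and 5 in the other, and 3/38 = 7.9% shows that 3 is right. Both copies give 5 for chronicity, but single digits here are not safe. With medians of 2 and 3, about 20% of simulated samples gave p of 0.15 or more. This stands, and is why the source check comes first.

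**The prognostic link is assumed.** The documents do not say that the index predicts eGFR, when the biopsies were taken (median disease duration is 6 to 7 years), or how many patients were scored. An old score may add little beyond baseline eGFR. This stands: it widens the range in the table above and leaves the extension to 24-hour protein without support.

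**Chance imbalance does not invalidate a randomised comparison, and picking this row after outcomes were tabulated is post hoc.** Both are true. The term is therefore conditional confounding, and the index belongs in a supportive analysis, not a new main one.

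**There is no model to add a covariate to.** Section 6 specifies no baseline-adjusted between-arm renal analysis, and Friedman and Mann-Whitney tests take no covariates. This stands, and the fix starts there.

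**Conclusion.** The point holds in limited form. The chronicity row is internally implausible and needs checking. If the imbalance is real, the eGFR and creatinine comparisons are conditionally confounded, because no renal analysis uses the index or the baseline value. The shift from the index alone is 0.6 to 12.8 ml/min against the drug on a baseline-adjusted scale. This rests on the assumed partial correlation and residual SD, and on which reading of the imbalance is right.

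Three stronger readings are tempting, and the documents do not support them:
- *The renal results are biased against the drug.* The higher starting eGFR in the study arm pulls the raw comparison the other way, and class IV is less frequent there (16 v 26). The net direction is open. Nor is the 15.4 ml/min gap at 12 months a fair yardstick, since 14 of it was present at baseline.
- *Leaving the index out wastes precision.* At the printed imbalance, adjustment costs precision over the whole assumed range. It helps only if the imbalance is small, and then the shift is small too.
- *Randomisation failed.* The tables cover 79 patients against 100 targeted, but the text does not say whether the shortfall arose before or after allocation.

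**What to change.** 1. Check the Table 2 chronicity medians, ranges and p-value against source data, and state how many biopsies in each arm were scored and when they were taken. Correct the table if a figure is wrong.
2. In SAP section 6, compare the arms on 12-month eGFR and on log creatinine with a model that includes the baseline value of that outcome.
3. Add a supportive analysis with the chronicity index as a further covariate. Justify it on prognostic grounds and not on the observed imbalance, label it as added after the data were seen, give a rule for unscored biopsies, and show the model without the index beside it.
4. Do not extend this to 24-hour protein unless a prognostic reason is given.

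The cost is a short new paragraph in section 6, a source check and a re-run. It is more than one line, because the baseline-adjusted model has to be specified first. The statistical price is one degree of freedom and, if the imbalance is as large as printed, an SE about 5 to 14% larger in the supportive analysis. What it buys is less conditional bias.
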